## **Statistical Considerations**

### ***Sample Size Calculation***

In this R15, sample size is based on reductions in breathlessness; a significant reduction of 1 SD, was found in the PI's previous interventions on end-stage HF breathlessness. A sample size of 30 (15 per group) is able to detect a reduction of 1.3 SDs with a Type 1 error rate of 0.05 and a power of 0.80 [31-33] To account for an expected 20% attrition (due to HF deaths), three additional families will be recruited to each group. Thus, there will be 18 patient-caregiver dyads per each group (total N=72; 36 patients and 36 caregivers).

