## **Statistical Analysis Plan**

Descriptive statistics (frequencies, means, standard deviations) will summarize the caregiver and patient characteristics and program implementation costs. A generalized linear model (GLM) will test for significant differences between the control and intervention groups in terms of health outcome scores measured at baseline and at 3 and 6 months, controlling for covariate effects. The GLM is the extended version of the general linear model applicable to variables that are not normally distributed and is commonly used in small sample studies [39]. The GLM also provides a post hoc analysis that yields results similar to those of t tests. A strength of GLM is that it also provides repeated data collection time factors in post hoc analyses. A one-tailed group comparisons will be used to test our *a priori* directional hypotheses using the

---

Bonferroni adjustment. [40]. Thus, this post hoc paired comparison between groups can reveal significant differences between outcomes at baseline vs. 3 months and at baseline vs. 6 months. The intent-to-treat statistical approach will be used, as all patients are included in the analysis with imputation means replacement [41]. Data analyses will be conducted using SPSS (version 29).

This study will use a traditional cost accounting method to calculate the cost of implementing FamPALcare. All expenses related to delivering the program will be tabulated. The cost of the clinician delivering the intervention will be calculated from an average of a nurse's hourly salary. The costs of educational materials given to participants in the manual will be tallied and summarized.

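### The sample size section cites an earlier 1 SD effect but states 80% power for 1.3 SD, and its effect, sample size, alpha and power do not fit together

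*Combined protocol and SAP*

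**What the plan says.** The Sample Size Calculation section states that "sample size is based on reductions in breathlessness". The one piece of prior evidence it offers is that "a significant reduction of 1 SD, was found in the PI's previous interventions on end-stage HF breathlessness". The next sentence says that 30 evaluable dyads, 15 per group, "is able to detect a reduction of 1.3 SDs with a Type 1 error rate of 0.05 and a power of 0.80". Three more per group are added for an expected 20% attrition, giving 18 per group. The section does not say whether alpha is one- or two-sided, whether it is divided among comparisons, or which SD is meant.

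The Statistical Analysis Plan section adds two facts that bear on power. "A one-tailed group comparisons will be used to test our" directional hypotheses, and these comparisons use the "Bonferroni adjustment". It describes contrasts of baseline with 3 months and baseline with 6 months. It does not give the number of comparisons in the family.

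**The concern.** Two consecutive sentences use two different effects. The evidence is 1 SD; the power is quoted for an effect 30% larger (1.3 / 1.0 = 1.3). The 80% is therefore not stated for the effect the plan cites, and no other section links the two figures.

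It matters for how a null result is read. Someone who takes 80% as the chance of confirming the 1 SD reduction could treat a non-significant result as evidence against a 1 SD effect. Whether that is fair depends on the power at 1 SD under the planned test, which the plan does not give. The plan also does not say whether the earlier 1 SD was a difference from control or a before-after change, although the trial will test differences between groups.

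**Working it through.** **Inputs.** From Sample Size Calculation: n = 15 per group, alpha 0.05, power 0.80, effects of 1.0 and 1.3 SD, 18 enrolled per group, 20% attrition. From Randomization and Blinding: 1:1 allocation. From Statistical Analysis Plan: one-tailed tests with Bonferroni adjustment, number of tests not given. I take the SD to be that of the analysed outcome and compare two means.

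**Method.** Noncentral t with 2n − 2 = 28 degrees of freedom and noncentrality d × √(n/2). The normal approximation, Φ(d√(n/2) − z), serves as a check that can be done by hand.

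**Step 1: the plan's own figure.** At d = 1.3 the noncentrality is 1.3 × √7.5 = 3.560.

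| Test, alpha 0.05, d = 1.3 | Normal check | Noncentral t |
|---|---|---|
| Two-sided | Φ(3.560 − 1.960) = 94.5% | 93.0% |
| One-tailed | Φ(3.560 − 1.645) = 97.2% | 96.6% |

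The printed 80% is not reproduced either way. By the t-test, 80% power at 1.3 SD would need about 11 per group two-sided or 9 one-tailed.

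**Step 2: the effect that 15 per group can detect.** By the normal approximation it is (z_alpha + 0.842) × √(2/15):
- Two-sided: 2.802 × 0.3651 = 1.02 SD; by the t-test, 1.06 SD.
- One-tailed: 2.486 × 0.3651 = 0.91 SD; by the t-test, 0.93 SD.

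At unadjusted alpha, 15 per group therefore matches an effect of about 1 SD, not 1.3 SD.

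**Step 3: power at the cited 1.0 SD, unadjusted.** The noncentrality is √7.5 = 2.739.
- Two-sided: Φ(2.739 − 1.960) = 78.2%; t-test 75.3%.
- One-tailed: Φ(2.739 − 1.645) = 86.3%; t-test 84.8%.

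**Step 4: power at 1.0 SD under the planned adjustment.** One-tailed t-test at alpha 0.05/k. The two time contrasts alone suggest k of at least 2. The Objectives section names two caregiver and two patient outcomes, each at 3 and 6 months, so k = 4 × 2 = 8 if all form one family. The values of k are assumptions. Attrition of 20% from 18 leaves 18 × 0.8 = 14.4 per group.

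| Tests, k | 15 per group | 14.4 per group |
|---|---|---|
| 1 | 84.8% | 83.4% |
| 2 | 75.3% | 73.4% |
| 4 | 64.6% | 62.4% |
| 8 | 53.5% | 51.2% |

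**Step 5: can the printed 80% be recovered?** A one-tailed alpha of 0.05/8 gives 80.6% at 1.3 SD; two-sided 0.05/4 puts the same 0.00625 in the tail and gives the same result. The section states 0.05 and mentions no division. A different SD could also lower the figure. If 1.3 is in units of a single measurement's SD and change scores are analysed, the SD of change is √(2(1 − r)) times larger, r being the correlation between baseline and follow-up. Two-sided power at 1.3 SD is then 82.7% for r = 0.3 and 68.1% for r = 0. The plan defines no SD and gives no correlation, so this too is only a possibility.

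**The case against.** The strongest reply is that the trial is not undersized for 1 SD. At the stated alpha and with the one-tailed test that the plan names, unadjusted power at 1 SD is 85%, above the 80% target, and 1.3 is the number that does not fit. This stands for an unadjusted test, and it is why the mismatch alone does not show a shortfall. It does not rescue the section: the printed 80% at 1.3 SD remains unsupported, and the planned test is adjusted.

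A second reply is that the size of the Bonferroni family is unknown, so 75%, 65% and 54% are the results of assumed values of k. This also stands; they are a range, not the trial's power. They further depend on about 15 evaluable per group: with 18 per group and two tests, power is 83.0%. But the plan itself expects 20% attrition, and replacing missing values by means adds no real information.

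Third, a plain t-test is not the covariate-adjusted repeated-measures model that is planned, and breathlessness is not named among the outcomes in the aims. Both limits are fair. The model's power cannot be computed from the documents, and none of these figures is the power for caregiver burden, depression/anxiety or HF-related health.

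Finally, the plan reports 1 SD as prior evidence and does not call it the design effect. That is true, but it is the only evidence given, and nothing supports 1.3 SD in its place.

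**Conclusion.** The point holds as an inconsistency in the stated figures. The section cites 1 SD, quotes power for 1.3 SD without explanation, and gives an 80% that does not follow from 15 per group at alpha 0.05, where the t-test gives 93% two-sided or 97% one-tailed. At the cited 1 SD, unadjusted power is 75% two-sided or 85% one-tailed. Under the one-tailed Bonferroni test it is 75%, 65% or 54% for two, four or eight tests, or 73%, 62% or 51% with 14.4 completers per group. These results assume a two-sample t-test and an SD that is that of the analysed outcome; the adjusted ones also assume the number of tests.

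A reader might infer that power at 1 SD is only 58–61%, by accepting 80% at 1.3 SD and scaling down: Φ(2.802/1.3 − 1.960) = 57.7% two-sided and Φ(2.486/1.3 − 1.645) = 60.6% one-tailed. The documents do not support that. The calculation never uses the stated 15 per group, and it starts from the one figure that fails to reproduce. Nor do they support a flat statement that the trial has too few dyads for 1 SD; that turns on the unstated number of comparisons.

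**What to change.** In the Sample Size Calculation section, replace the statement of 80% power at 1.3 SD with a figure that follows from 15 per group, the one-tailed test and the per-comparison alpha actually planned. In the same place, state:

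- which effect is the design effect and, if it is not 1 SD, why;
- how the SD is defined, and whether the earlier 1 SD was a between-group difference or a before-after change;
- the number of comparisons in the Bonferroni family;
- the resulting power at a 1 SD group difference and, if it is below 80%, that a non-significant result does not exclude an effect of that size.

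The sponsor should take the number of comparisons from its own analysis plan; the values of two, four and eight used here only show the range. The planned 36 dyads can stay. The change is to protocol wording only and needs no more participants; the one drawback is that the stated power may be less favourable.

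### The 1.3 SD detectable effect does not follow from its stated inputs (15 per group, Type 1 error 0.05, power 0.80), and the input behind it is not given

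*Combined protocol and SAP*

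**What the plan says.** The Sample Size Calculation section bases the trial on breathlessness. It reports that in earlier work "a significant reduction of 1 SD, was found", and then states: "A sample size of 30 (15 per group) is able to detect a reduction of 1.3 SDs". The alpha and power attached to this claim are given as "with a Type 1 error rate of 0.05 and a power of 0.80". It names no test, no sidedness and no multiplicity adjustment. It also does not say whether the SD is that of baseline, outcome or change.

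On losses it says: "To account for an expected 20% attrition (due to HF deaths), three additional families will be recruited to each group". This gives 18 dyads per group and 36 in all.

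The Statistical Analysis Plan section supplies some of what is missing, but does not tie it to the sample size. It says "A one-tailed group comparisons will be used to test our" directional hypotheses, and it refers to the "Bonferroni adjustment. [40]. Thus, this post hoc paired comparison between groups can reveal significant differences". The contrasts that it lists are those "between outcomes at baseline vs. 3 months and at baseline vs. 6 months". The number of comparisons to be adjusted for is not given. The model is fitted "controlling for covariate effects", without naming the covariates, and every patient is analysed, with missing values replaced by means.

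The Objectives section names two caregiver outcomes (burden; depression/anxiety) and two patient outcomes (HF-related health; depression/anxiety), each at 3 and 6 months.

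**The concern.** A detectable effect, a group size, an alpha and a power are linked: once three are fixed, the fourth follows. Here all four are stated and they do not agree. Either 1.3 SD is larger than the design needs, or one of the other inputs is not the one actually used.

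This matters because the paragraph sets a detectable effect of 1.3 SD beside an earlier effect of 1 SD. A reader will want the power at 1 SD, and cannot get it. If alpha is a plain one-tailed 0.05, that power is good. If 1.3 SD already reflects a Bonferroni-adjusted alpha, it is only about a half. A null result would be read differently in the two cases.

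**Working it through.** **Inputs.** From Sample Size Calculation: n = 15 per group, alpha 0.05, power 0.80, effect 1.3 SD, earlier effect 1 SD, attrition 20%, 18 enrolled per group. From Randomization and Blinding: 1:1 allocation. From Statistical Analysis Plan: one-tailed tests, Bonferroni, divisor not stated. Assumed: a two-sample t-test on means with SD = 1.

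**Formula.** Power = P(T > t_crit), where T is noncentral t with df = 2n − 2 and noncentrality d·√(n/2).

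**1. The plan's own figure.** With n = 15, df = 28 and √(15/2) = 2.739. At d = 1.3 the noncentrality is 1.3 × 2.739 = 3.560.
- One-sided 0.05: t_crit = 1.701, power 96.6%.
- Two-sided 0.05: t_crit = 2.048, power 93.0%.

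Neither is 80%.

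**2. Detectable effect at 80% power, n = 15.** Solving for d gives 0.931 SD (one-sided) or 1.060 SD (two-sided). The normal approximation agrees: (1.645 + 0.842) × √(2/15) = 0.91 and (1.960 + 0.842) × √(2/15) = 1.02. Allowing for the efficiency of a Wilcoxon test (0.864 at worst) raises the values only to 1.00 or 1.14 SD.

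**3. Group size needed for 1.3 SD at 80% power.** One-sided: 8 per group gives 79.6% and 9 gives 84.0%, so 9. Two-sided: 10 gives 78.5% and 11 gives 82.6%, so 11. The plan has 15.

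**4. What would give about 1.3 SD with 15 per group.** Each route needs an input that the section does not state:
- One-sided alpha 0.05/8: 1.292 SD, with 80.6% power at 1.3 SD. The divisor 8 would be four outcomes × two times.
- Two-sided alpha 0.01: 1.327 SD.
- Two-sided alpha 0.05 with power 0.93: 1.300 SD.
- Change scores expressed in baseline SDs, multiplying by √(2(1 − r)): 1.060 × √1.5 = 1.298 SD (two-sided, r = 0.25), or 0.931 × √1.96 = 1.303 SD (one-sided, r = 0.02).

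**5. Attrition.** 18 × 0.80 = 14.4 per group with observed data. Keeping 15 would need 15/0.80 = 18.75. Adding three is 20% of 15, not an allowance for losing 20% of those enrolled. The gap is 0.6 of a dyad per group.

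**6. Effect of the divisor.** One-tailed alpha 0.05/k, unadjusted t-test:

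| k | n = 15: SD at 80% power | n = 15: power at 1 SD | n = 14: SD at 80% power | n = 14: power at 1 SD |
|---|---|---|---|---|
| 1 | 0.93 | 85% | 0.97 | 82% |
| 2 | 1.06 | 75% | 1.10 | 72% |
| 4 | 1.18 | 65% | 1.23 | 61% |
| 8 | 1.29 | 54% | 1.34 | 50% |

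k = 2 reads the plan as two comparisons per outcome (3 and 6 months, each against baseline). k = 8 reads it as all four outcomes at both times.

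**7. Effect of baseline adjustment.** The documents give no baseline–outcome correlation r, so this is an assumed range. With n = 14, SD multiplied by √(1 − r²) and df = 2n − 3, power at 1 SD for k = 1, 2, 4, 8 is 91%, 84%, 74%, 64% at r = 0.5, and 97%, 95%, 90%, 83% at r = 0.7.

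**The case against.** Five things can be said for the plan.

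- **Taken literally, the sentence is not false.** If power at 1.3 SD is 93% to 97%, then 15 per group does detect 1.3 SD with at least 80% power. This stands: at an unadjusted 0.05 the figure errs on the safe side. But 0.80 is given as the power of the calculation, and it is not the power that those inputs produce.
- **The plan's own testing rule nearly returns 1.3 SD.** One-tailed Bonferroni over four outcomes at two times gives 1.29 SD, and this is the only route in step 4 built entirely from elements in the documents. A reader might infer that this is where 1.3 SD came from, and that the design has no spare power. The documents do not support so firm a conclusion: the stated Type 1 error is 0.05, no divisor appears anywhere, and breathlessness is not among the four outcomes.
- **The method may lie in the references cited after the calculation.** Possibly so, but the paragraph should still state its own inputs.
- **The planned analysis is not a t-test on 14 completers.** It includes all patients, with mean imputation and covariate adjustment. At a nominal 18 per group, k = 1, 2, 4, 8 gives 0.85, 0.96, 1.07, 1.17 SD and 90%, 83%, 74%, 64% power at 1 SD. This objection stands as to labelling. Replaced means add no real information, so the figures for 18 are optimistic; those for 14 ignore a gain that covariate adjustment may bring.
- **The attrition gap is trivial.** It is small, but it is corrected in the same sentence.

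**Conclusion.** The mismatch is real. For a two-group comparison of means, the stated inputs give 0.93 or 1.06 SD, not 1.3 SD, and power at 1.3 SD is 97% or 93%, not 80%. Neither sidedness nor the choice between a t-test, a normal approximation and a Wilcoxon test closes the gap. The figure is conservative if alpha is an unadjusted 0.05 and about exact if it is a one-tailed 0.05/8; the documents do not say which. Separately, the expected number with observed data is about 14 per group, not 15.

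A reader might go further and infer from 1.3 SD exceeding the earlier 1 SD that the trial is too small. The documents do not support that. Power at 1 SD with 14 per group runs from 50% (k = 8, unadjusted) to 97% (k = 1, baseline-adjusted, assumed r = 0.7). That width reflects missing inputs, not a demonstrated shortfall. The range also assumes that the earlier 1 SD was a between-group difference, which is not stated.

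**What to change.** Keep 36 dyads and restate the paragraph with the inputs that produce its figure, in one of two ways.

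- **If the powered comparison is not Bonferroni-adjusted:** replace 1.3 SD with 0.93 SD for 15 per group at one-tailed 0.05, or 1.06 SD if two-sided.
- **If the Bonferroni adjustment applies to it:** state the divisor k and give the matching n = 14 row of the table in step 6. For example, with k = 2: *Eighteen dyads per group will be enrolled, and after 20% attrition about 14 per group should have observed data. In an unadjusted two-sample t-test at one-tailed 0.05/2, 14 per group gives 80% power for 1.10 SD and 72% power for a between-group difference of 1 SD.*

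Whichever is chosen:
- label the figures as unadjusted t-test values;
- note that the planned analysis set is all 18 per group with mean imputation, which adds no real information, and that adjusting for baseline, if it is a covariate, would raise power;
- correct the attrition sentence to about 14 per group;
- say which SD is meant, and whether the earlier 1 SD was a between-group difference or a within-group change.

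If 1.3 SD is kept, state the input that yields it.

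The cost is one rewritten paragraph. Enrolment and data collection do not change. Stating k does settle an analysis choice that is now open, but the Bonferroni tests cannot be run without it. The downside is that the restated power may look less favourable.

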## Introduction

### Background and Rationale

Heart failure (HF) affects more than 8 million Americans and is increasing at a rate of 46%, with an increase in costs of up to \$70 billion annually [1]. Severe symptoms of HF persist despite medical, surgical, or HF device therapy [2]. HF is a debilitating and life-limiting disease that requires extensive home family caregiving assistance and difficult decisions regarding treatment options for patients who are experiencing progressive decline [3, 4]. Studies verify family caregivers contributions to HF home care. Worsening HF has numerous negative impacts on family caregiver health outcomes, resulting in caregiving burden [3, 5]. In turn, the caregiving burden can have a negative impact on caregiver's physical and mental health status [5]. Family caregivers managing patient HF reported unmet needs, [6] lack of communication with health care professionals, [7] and little if any preparedness for home end-of-life and palliative care (EOLPC) [8].

Patients and their families are unprepared for the challenges of this deteriorating condition and for home caregiving burdens. Most have fears of suffering a painful death [9, 10]. Our nurse-led family home EOLPC intervention (FamPALcare) addresses these challenges [11]. Palliative care includes supportive and comfort care to relieve patient suffering and pain/discomfort [12]. HF palliative care also includes treatments specific for the distressing, commonly repeating physical and psychological symptoms of HF (e.g., breathlessness, fatigue, edema, and depression/anxiety). HF palliative care includes discussions for determining the HF care options according to the families' end-of-life (EOL) care preferences [13].

Further, patients with HF who live in rural areas have higher mortality rates than those who live in urban areas [14]. Specifically, in West Virginia (WV), where HF death rates are the highest in the country, residents have limited access to healthcare and experience social service inequities [15, 16]. The rural mountainous terrain and distance from HF specialists and local healthcare services increase the family caregivers' need for more useful home care information [17]. Home palliative care interventions can assist families in managing advancing HF symptoms and end-of-life (EOL) care needs at home [18].

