## Objectives

The following specific aims, directional hypotheses, and research questions are:

**Primary Aim:** To test whether the FamPALcare nursing care intervention could reduce the burden of family caregivers by preventing caregiver depression/anxiety and improve patient HF-related health status and depression/anxiety. The hypotheses and research questions are as follows:

*Aim 1.1* Compared to those in the control group at 3 and 6 months, the caregivers who receive FamPALcare will have significant improvements in home caregiving burden and depression/anxiety scores.

*Aim 1.2* Compared to those in the control group at 3 and 6 months, patients in the FamPALcare group will experience greater improvement in HF-related health and depression/anxiety scores.

**Secondary Aim:** To assess the feasibility and fidelity of the FamPALcare intervention.

*Aim 2.1.* What are the participant recruitment, enrollment, and retention outcomes?

*Aim 2.2.* How helpful the FamPALcare as rated by participants on the anonymous 11-item Helpfulness Questionnaire?

*Aim 2.3.* What is the FamPALcare implementation cost using traditional tabulated cost-minimization analysis?

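### The stated 80% power for 1.3 SD does not follow from its printed inputs, cannot be matched to the Bonferroni threshold in the analysis plan, and rests on breathlessness, which Aim 1 does not name

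*Combined protocol and SAP*

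**What the plan says.** The Sample Size Calculation section contains the plan's only power statement. It says that "sample size is based on reductions in breathlessness", and that "a significant reduction of 1 SD, was found in the" investigator's earlier interventions. It then states that 15 per group "is able to detect a reduction of 1.3 SDs with a Type 1 error rate of 0.05 and a power of 0.80". The sentence does not say whether the test is one- or two-sided, whether 0.05 is per test or familywise, or whether the SD refers to single, change or adjusted scores. On losses it says: "To account for an expected 20% attrition (due to HF deaths), three additional families will be recruited to each group". That makes 18 dyads per group.

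The Statistical Analysis Plan section models "health outcome scores measured at baseline and at 3 and 6 months, controlling for covariate effects". It specifies one-tailed group comparisons with a Bonferroni adjustment and looks at baseline against 3 months and baseline against 6 months. It does not say how many tests the adjustment covers.

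Under Objectives, Aim 1.1 expects that "the caregivers who receive FamPALcare will have significant improvements in home caregiving burden and depression/anxiety scores", and Aim 1.2 expects that "patients in the FamPALcare group will experience greater improvement in HF-related health and depression/anxiety scores". That is four outcomes at two time points. Breathlessness is not named among them.

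**The concern.** A power statement should let a reader recompute it and should refer to the test that will be run. This one does neither. Its printed inputs give a clearly different power, and the threshold in the analysis plan cannot be calculated because the size of the Bonferroni family is missing.

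Two things are at stake. The first is the reading of a null result: at 1 SD, the only prior effect cited, power ranges from comfortable to a coin toss depending on the family size. The second is the test itself. If the family is settled after results are seen, the choice can change which outcomes are declared significant. In addition, the one effect size offered concerns a symptom outside the named Aim 1 outcomes.

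**Working it through.** **Inputs.** From the Sample Size Calculation: n = 15 per group, effect 1.3 SD, Type 1 error 0.05, stated power 0.80, prior effect 1 SD, attrition 20%, 18 recruited per group. From the Statistical Analysis Plan: one-tailed, Bonferroni, family size m not given. From Objectives: four outcomes at 3 and 6 months. Assumed here: m = 1, 2, 4 or 8, and a baseline-to-follow-up correlation r where one is needed.

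**Formula.** For two groups of n compared on single scores, power is the probability that a noncentral t with 2n − 2 degrees of freedom and noncentrality d × √(n/2) exceeds the critical value.

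**Step 1: the plan's own figure.** Noncentrality = 1.3 × √(15/2) = 3.56, with 28 degrees of freedom.
- One-tailed 0.05: critical value 1.701, power 96.6%.
- Two-sided 0.05: critical value 2.048, power 93.0%.
- The effect at which 80% power is reached is 0.93 SD one-tailed and 1.06 SD two-sided.

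So 0.80 is not reproduced.

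**Step 2: readings that do give about 80%.** All are at 15 per group.
- 0.05 familywise over eight one-tailed tests (4 outcomes × 2 times; 0.05/8 = 0.00625): critical value 2.669, power 80.6%. The count of eight is made here, not by the plan.
- 0.05 familywise over four two-sided tests (0.0125): 80.6%, with the same critical value.
- Change scores in baseline SD units, effective d = 1.3/√(2(1 − r)): one-tailed at r = 0, d = 0.919 and power 79%; two-sided at r = 0.2 to 0.3, power 78% to 83%.

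These are different designs, and the section does not say which was used, if any.

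**Step 3: completers.** 18 × 0.8 = 14.4, slightly under the 15 the power sentence relies on; 15/0.8 would be 18.75. The figures below use 14. Replacing missing values by means keeps 18 per group nominally, but an imputed mean adds no information about the group difference.

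**Step 4: power at the planned kind of threshold.** One-tailed, 14 per group, single scores, no baseline adjustment:

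| Tests in family | Per-test alpha | Power, 1.3 SD | Power, 1 SD | Effect with 80% power |
|---|---|---|---|---|
| 1 | 0.05 | 96% | 82% | 0.97 SD |
| 2 | 0.025 | 91% | 72% | 1.10 SD |
| 4 | 0.0125 | 85% | 61% | 1.23 SD |
| 8 | 0.00625 | 77% | 50% | 1.34 SD |

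**Step 5: baseline adjustment.** Effective d = d/√(1 − r²), degrees of freedom 2n − 3 = 25. With an assumed r of 0.5 to 0.7 the multiplier is 1.155 to 1.400. For eight tests, power is then 89% to 98% for 1.3 SD and 64% to 83% for 1 SD.

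**The case against.** The strongest reply is that the sentence may be right. One-tailed testing and Bonferroni are both in the analysis plan, and four outcomes at two times are in the Objectives. If 0.05 is the familywise rate over those eight tests, single scores give 80.6%. Nothing in the documents excludes this, and the references cited at that sentence cannot be seen here. So a reader who infers that the sponsor miscalculated goes further than the documents allow. What stands is that the section does not state this reading, and that other unstated readings fit about as well.

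Second, eight is not the plan's number. Its two time contrasts make a family of two at least as natural, and there power for 1.3 SD is 91% even at 14 completers. Baseline adjustment, which the analysis plan may intend, would raise power further. This is accepted, and it is why a range is shown.

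Third, sidedness is not missing from the plan as a whole: the Statistical Analysis Plan says one-tailed. Only the power sentence is silent.

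Fourth, a standardised effect has no scale, so 1.3 SD on a caregiver score has the same power at the same n and alpha. Sizing a small trial on one outcome is also common. Breathlessness may sit within patient HF-related health, since the Background lists it among the "physical and psychological symptoms of HF (e.g., breathlessness, fatigue, edema, and depression/anxiety" symptoms that palliative care treats. This is fair. The gap is narrower: no instrument links breathlessness to an Aim 1 outcome, and no reason is given to expect 1.3 SD, or 1 SD, on any of the four. Attrition is also attributed to HF deaths, so applying 14 completers to caregiver scores is a further assumption.

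**Conclusion.** The point holds as a mismatch and a gap in the plan. At the printed 0.05, the printed inputs give 97% (one-tailed) or 93% (two-sided) rather than 80%, so the statement is cautious for a single unadjusted test of single scores. It cannot be matched to the Bonferroni threshold, because the family size is not given. It assumes 15 completers where the recruitment figure yields 14.4, and its effect size comes from an outcome that Aim 1 does not name.

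A reader might infer that the trial is too small for 1.3 SD. The documents do not support that: among the families considered, power at 14 completers falls below 80% only with eight tests and no baseline adjustment (77%). Nor does the plan claim 80% at 1 SD; the lower figures there describe what the cited prior effect would give.

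The 97%, 93% and 14.4 follow from the plan's numbers and the test named. Every adjusted figure depends on an assumed family size, and the baseline-adjusted and change-score figures also on an assumed r. This should be fixed, but it does not invalidate the design.

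**What to change.** In the Sample Size Calculation, restate power at the one-tailed Bonferroni threshold of the Statistical Analysis Plan and at 14 completers per group. Give the family size, the per-test alpha, and whether scores are single, change or baseline-adjusted, with the assumed correlation where one is used. State the same family size in the Statistical Analysis Plan. The sponsor should choose the family and fix it before results are seen by group; the table in the working supplies the unadjusted figures for two, four or eight tests.

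Example wording for a family of two: each test is one-tailed at 0.025; with 18 dyads per group and 20% attrition, 14 per group are expected; without baseline adjustment, power is 91% for 1.3 SD and 72% for 1 SD, and 80% power is reached at 1.10 SD. For a family of eight, the alpha is 0.00625 and the figures are 77%, 50% and 1.34 SD.

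Add a sentence saying that the 1 SD prior effect comes from breathlessness and is not evidence for the Aim 1 outcomes.

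The cost is wording only, with no added enrolment. The downside is disclosure: without baseline adjustment, the stated power at 1 SD falls below 80% once two or more tests are adjusted for.

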### *Randomization and Blinding*

This RCT uses random assignment to group with stratification of the patient sex (male vs female) to equalize distribution. SPSS version 29 is used to generate random numbers within each group. Each family dyad is randomly assigned to either the control or intervention group in a 1:1 fashion [11]. The researchers are blinded to the group assignments until informed consent is obtained. The Institutional Review Board of the University Health Sciences Center (WVU IRB 1709754988) approved the study protocol.

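### The three extra families per group cover 16.7% attrition, not the stated 20%: a 20% loss from 18 leaves 14.4 dyads per group, slightly below the 15 used for power

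*Combined protocol and SAP*

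**What the plan says.** The Sample Size Calculation section of the combined protocol and SAP starts from an evaluable number: "A sample size of 30 (15 per group) is able to detect a reduction of 1.3 SDs". For this it sets alpha at 0.05 and power at 0.80, and it does not give the sidedness. It then adds the allowance for losses: "To account for an expected 20% attrition (due to HF deaths), three additional families will be recruited to each group". The enrolled number that follows is 18 dyads per group, or 36 dyads and 72 persons in all.

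The Randomization and Blinding section makes the dyad the unit of allocation, in a 1:1 ratio. The Statistical Analysis Plan section plans one-tailed tests of its directional hypotheses, with a Bonferroni adjustment whose number of comparisons is not stated. It also keeps all patients in the analysis by replacing missing values with means.

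**The concern.** The section shows no formula, but the step from 15 to 18 is exactly 15 × 1.2. That takes the 20% as a share of the evaluable number. Attrition removes a share of those enrolled, so the evaluable number has to be divided by the retained fraction, 0.80.

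What is at stake is whether the enrolled number delivers the 15 per group to which the plan attaches its power. The expected losses are deaths from heart failure, so better follow-up would not recover them. A reader who takes the paragraph at its word would believe that 15 per group are expected to remain, and on the plan's own figures they are not.

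**Working it through.** **Inputs** (all from Sample Size Calculation unless noted): 15 evaluable dyads per group; expected attrition 20%; three families added per group; 18 enrolled per group; target effect 1.3 SD; alpha 0.05; power 0.80. One-tailed testing and the Bonferroni adjustment come from Statistical Analysis Plan.

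**1. The plan's enrolled number.** n × (1 + d) = 15 × 1.20 = 18. This reproduces the stated figure exactly.

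**2. What 18 leaves.** n × (1 − d) = 18 × 0.80 = 14.4, which is 15 − 14.4 = 0.6 dyad short per group.

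**3. What 18 covers.** 3/18 = 16.7%.

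**4. What 20% would need.** n / (1 − d) = 15/0.80 = 18.75, so 19 per group. Check: 19 × 0.80 = 15.2.

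**5. Effect on power and detectable difference.** Two-sample t test with n per group, 2n − 2 degrees of freedom and noncentrality δ × √(n/2). For δ = 1.3 SD the noncentrality is 1.3 × √7.5 = 3.56 at n = 15, 1.3 × √7.2 = 3.49 at n = 14.4, and 1.3 × √7 = 3.44 at n = 14. At an unadjusted alpha of 0.05:

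| n per group | SD detectable with 80% power, one-sided | SD detectable with 80% power, two-sided | Power for 1.3 SD, one-sided | Power for 1.3 SD, two-sided |
|---|---|---|---|---|
| 15 | 0.93 | 1.06 | 0.966 | 0.930 |
| 14.4 | 0.95 | 1.08 | 0.960 | 0.919 |
| 14 | 0.97 | 1.10 | 0.956 | 0.911 |

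The first row does not reproduce the stated power of 0.80 for 1.3 SD with 15 per group. At that alpha, about 9 per group (one-sided) or 11 (two-sided) would be enough for 1.3 SD. This is a separate inconsistency in the same paragraph. It matters here because it leaves room on the stated inputs.

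**6. Sensitivity to the Bonferroni divisor.** The documents give no divisor, so the values below are assumptions. One-sided power for 1.3 SD:

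| Assumed alpha | n = 15 | n = 14.4 | n = 14 |
|---|---|---|---|
| 0.05/4 | 0.876 | 0.860 | 0.848 |
| 0.05/6 | 0.837 | 0.817 | 0.803 |
| 0.05/8 | 0.806 | 0.784 | 0.768 |

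**7. Chance of ending below 15.** Assume that each dyad is lost independently with probability 0.20. With 18 enrolled, a given group ends with 14 or fewer with probability 0.50, and at least one of the two groups does so with probability 1 − (1 − 0.499)² = 0.75. With 19 enrolled the figures are 0.33 and 1 − (1 − 0.327)² = 0.55. The part due to the slip is therefore about 0.75 − 0.55 = 0.20; the rest is chance variation that 19 per group would also carry.

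**The case against.** The strongest reply is that nothing of substance is lost. The gap is 0.6 dyad per group, the correction would be one dyad per group, and the detectable effect moves by 0.02 to 0.04 SD. On the stated 1.3 SD and alpha 0.05, power at 14 per group is still 0.91 two-sided and 0.96 one-sided. This stands, and it is why the point is minor. It does not make the sentence correct: the paragraph says that the three families account for 20% attrition, and they account for 16.7%.

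A second reply is that all patients stay in the analysis through mean replacement, so 18 per group are analysed. This does not stand. Imputed means do not restore the information lost with missing outcomes, and the sample-size paragraph itself treats attrition as a loss that extra recruits must make good.

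In the other direction, a reader might infer that the slip takes power below the stated 0.80. The documents do not support that. A fall below 0.80 appears in the working only at a one-sided 0.05/8, a divisor that neither the Sample Size Calculation nor the Statistical Analysis Plan section gives, and that attracts attention because it nearly reproduces the stated 1.3 SD with 15 per group. With 0.05/6, power at 14 per group is still 0.803. A reader might also take the 0.75 chance that at least one group ends below 15 as the cost of the slip; the same chance with 19 per group is 0.55.

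**Conclusion.** Wrong as written, and minor. The stated 20% allowance does not follow from the document's own numbers: 18 per group covers 16.7% attrition and leaves 14.4 dyads per group at 20%. This part needs no assumption beyond reading attrition as a share of those enrolled.

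The consequence is a slightly larger detectable effect. At an unadjusted alpha of 0.05, power for 1.3 SD stays above 0.90 at 14 per group. These figures assume a two-sample t test on complete dyads. What remains open is the effect under the Bonferroni adjustment, which cannot be fixed until the number of comparisons is given.

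**What to change.** Change one sentence in Sample Size Calculation, in one of two ways:

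- State that 18 dyads per group allows for 16.7% attrition; or
- Keep the 20% and state that about 14 dyads per group are then expected, with the detectable effect for that number at the alpha and sidedness actually used, including the Bonferroni divisor if it applies.

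Neither option needs extra dyads. The only cost is that the stated figure becomes slightly less favourable. The second option is best done together with a restatement of how 15 per group, 1.3 SD, alpha 0.05 and power 0.80 fit together, since both need the same alpha and sidedness.
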